9.0 Study Withdrawal/Discontinuation

Patients who wish to be withdrawn from the study for any reason will notify the PI or other study personnel. Patient data that have not been used or analyzed prior to this notification will be deleted from the REDCap database.

10.0 Statistical Considerations

As there are no current data on (or estimates of) the differences in PTT between rest and exercise, there is no formal power calculation to determine sample size. We will aim for a cohort of 15 participants, realizing that there may be a 'learning curve' that could render data from the initial participants unable to be used in quantitative analyses.

The primary analysis will consist of an intra-individual comparison of pre- and post-exercise PTT and PBV. As these will be paired observations that will likely not be normally distributed, the Wilcoxon matched-pairs signed rank test will be used for this evaluation. Similar methodology will be used to analyze the vein-to-heart times pre- and post-exercise. Bland-Altman analysis will be used to compare PTT obtained by two different techniques (intensity-time curves and visual assessment).

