2.0 Rationale and Specific Aims

While PTT in patients at rest has been successfully measured via contrast-echocardiography, whether post-exercise data can be reliably obtained and analyzed is unclear. Therefore, we propose to conduct a feasibility study to achieve the following aims:

1. Record the flow of ultrasound contrast across the pulmonary circulation after a standardized exercise protocol
2. Compare PTT and PBV pre- and post-exercise in the same cohort
3. Compare the time from contrast administration to appearance in the right-heart pre- and post-exercise (i.e. vein-to-heart time)
4. Compare PTT obtained by analysis of time-intensity curves to the PTT estimate obtained by visual assessment

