6.0 Study Procedures

All study procedures will take place over a single day during a single visit to the CRC. Participants will experience the following:

1. **Baseline demographics and anthropomorphic measurements.** Basic information on age, gender, and self-identified ethnicity will be collected along with height and weight.
2. **Pre-exercise echocardiographic evaluation.** This assessment will be performed by the CRC sonographer and will include heart rate, LVOT diameter, LVOT VTI, mitral valve inflow, mitral valve tissue Doppler imaging, IVC size/respirophasic changes in caliber, and a recording of the apical 4-chamber

- view (the view in which contrast flow will be recorded) to ensure adequate visualization.
3. **Pre-exercise PTT measurement.** Following placement of a standard peripheral IV by a CRC nurse, ultrasound contrast will be administered and the pathway of the contrast from entry into the right-heart through appearance in the left-heart will be recorded in order to obtain the data necessary to measure PTT. The interval between the beginning of the contrast injection and the appearance in the right-heart will be recorded. The IV line will then be flushed with saline to remove any residual contrast. After the acquisition of these data, the 'FLASH' feature of the ultrasound machine will be employed to rapidly remove the remaining contrast from the field of view such that there is minimal, if any, residual contrast when it is time for administration of contrast post-exercise.
 4. **Exercise protocol.** Participants will exercise on a treadmill (provided by the Metabolic Core) following a Standard Bruce Protocol until their heart rate reaches ~ 2.5-times their baseline level or until they reach maximum effort. Exercise capacity, blood pressure, and heart rate will be recorded at standard intervals throughout exercise. If it proves to be more logically favorable, an exercise bicycle (also supplied by the Metabolic Core) can be used rather than a treadmill.
 5. **Post-exercise PTT measurement.** This administration of contrast will be similar to the pre-exercise PTT measurement and will occur as soon as an adequate echocardiographic image can be obtained following exercise. Heart rate will also be recorded during this step. Mitral valve inflow, mitral valve tissue Doppler imaging, and IVC size/respirophasic changes in caliber will be re-assessed as well.

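### Must Section 10.0 commit to an estimate of the pre/post change beside the signed-rank test?

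*Combined protocol and SAP*

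**What the plan says.** Aim 2 in Section 2.0 is to "Compare PTT and PBV pre- and post-exercise in the same cohort"; Aim 3 does the same for vein-to-heart time. Section 10.0 carries these aims into the analysis: "The primary analysis will consist of an intra-individual comparison of pre- and post-exercise PTT and PBV". Because the observations are paired and unlikely to be normal, "the Wilcoxon matched-pairs signed rank test will be used for this evaluation". For the third measure, "Similar methodology will be used to analyze the vein-to-heart times pre- and post-exercise".

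The section gives no power calculation, on the ground that "there are no current data on (or estimates of) the differences in PTT between rest and exercise". It aims for 15 participants and accepts that early technical difficulty "could render data from the initial participants unable to be used in quantitative analyses". The only planned analysis that yields an estimate is for Aim 4: "Bland-Altman analysis will be used to compare PTT obtained by two different techniques". No section mentions a median change, a mean change, an interval or a descriptive summary for the pre/post comparisons.

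**The concern.** The plan says that nobody knows the size of the rest-to-exercise difference, then specifies a procedure whose named output is a p-value. Section 1.0 presents the work as groundwork for later studies, and those will need the size and precision of the change.

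For PTT the p-value may also be nearly a foregone conclusion. Section 6.0 has participants exercise "until their heart rate reaches ~ 2.5-times their baseline level or until they reach maximum effort". If PTT equals PBV divided by flow, higher flow alone would shorten it. When every participant's value falls, the signed-rank p-value sits at its minimum and cannot tell a moderate fall from a large one. If only that p-value were published, the study would not have supplied the missing quantity.

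**Working it through.** The plan states no effect size, SD, significance level or power, so there is no figure of its own to reproduce. The questions are how uninformative the test could be, and whether the estimate can be recovered from the planned data.

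**Inputs.** From Section 10.0: at most 15 pairs and the signed-rank test. Assumed, because the documents do not give them: two-sided 5% level; PTT = PBV/flow with PBV unchanged, so PTT ratio = 1/flow ratio; baseline PTT 5 s with log SD 0.2; SD of the log change 0.2 to 0.4.

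**1. The floor.** The smallest exact two-sided p-value is 2/2^n. At n = 15 this is 2/32,768 = 6.1e-5.

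**2. How often it is reached for PTT.** Results of 20,000 simulated trials per setting, n = 15, for SD 0.2 / 0.3 / 0.4:

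| Flow ratio | PTT ratio | Test rejects | p at floor |
|---|---|---|---|
| 1.3 | 0.77 | 99 / 79 / 49% | 22 / 4 / 1% |
| 1.5 | 0.67 | 100 / 99 / 87% | 72 / 26 / 8% |
| 1.67 | 0.60 | 100 / 100 / 97% | 93 / 51 / 21% |
| 2.0 | 0.50 | 100 / 100 / 100% | 99.6 / 85 / 53% |
| 2.5 | 0.40 | 100 / 100 / 100% | 100 / 98 / 85% |

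With small variation and a large fall, the p-value carries almost no information on size. With SD 0.4 and a ratio of 0.60 to 0.67, it is at the floor in only 8 to 21% of trials. The heart-rate target does not settle which row applies, because contrast is injected only once an adequate image is available after exercise, and flow at that moment is not fixed.

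**3. Can the size be recovered?** Yes. The Hodges-Lehmann estimate is the median of the n(n+1)/2 pairwise averages of the differences, and its interval comes from inverting the same test. At n = 15 there are 15 × 16/2 = 120 averages. The interval runs from the 26th to the 95th, at an exact level of 95.2%. At n = 12 the level is 95.7%, at n = 10 it is 95.1%, and at n = 6 it is 96.9%. At n = 5 the best available level is 1 − 2/2^5 = 93.75%, so no exact 95% interval exists there.

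With normal differences the average half-width is about 0.56 SD of the paired difference at n = 15, 0.66 at n = 12 and 0.71 at n = 10. In seconds, with SD 0.2, the median result is −1.6 (−2.1 to −1.2) at ratio 0.67 and −3.0 (−3.4 to −2.6) at ratio 0.40. The estimate separates cases that the p-value may not.

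**4. Would it alter a conclusion?** No. On the same scale, test and interval agreed in every simulated data set.

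**5. Is anything lost by not naming it?** No. Section 6.0, steps 3 and 5, records the contrast passage from which PTT is read before and after exercise, and Section 12.0 keeps the data for at least six years. The differences can be summarised at any time.

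**The case for a change.** The strongest reply is that a plan should fix its estimates before the data are seen, that one sentence would do it, and that the cost is close to nothing. It is fair that the plan does not commit to reporting the size of the change, and fair that this size is what a later study would use. Reporting a paired estimate with its interval and the number of pairs would be good practice.

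Less of the argument stands once the consequence is examined. It needs the investigators to publish a p-value and nothing else, which no section says; naming a test in a two-paragraph statistics section is not a list of everything to be reported. The numerical case is made for PTT alone. It does not carry over to PBV, where higher flow gives no reason to expect a fall, and no calculation supports it for vein-to-heart time. Its most striking figures come from the smallest assumed SD.

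The choice of estimate is also partly taste. Hodges-Lehmann matches the test but assumes roughly symmetric differences; other paired estimates with an interval would serve. A promised exact 95% interval could not be met with five or fewer usable pairs. For PBV, under PBV = PTT × flow, an estimate needs post-exercise flow, and step 5 of Section 6.0 does not list the LVOT VTI that step 2 records. That is a measurement question affecting the PBV test just as much, and naming an estimate would not resolve it.

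Nor would an estimate of the PTT change explain its cause: a ratio of 0.60 arises from 1.5/2.5 (PBV up 50%, flow 2.5 times) and equally from 1/1.67 (PBV unchanged).

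**Conclusion.** The omission is real, but it is a reporting gap that analysts would ordinarily fill, not a flaw in the plan. Followed exactly, Section 10.0 gives a sound paired test whose conclusion a matching interval could not reverse (agreement in 100% of simulated trials). No data are lost, and neither the target of 15 nor the choice of test is in question. The worry about an uninformative p-value is confined to PTT. Its size depends on assumptions outside the documents: at a PTT ratio of 0.67, the share of trials at the floor runs from 72% at SD 0.2 to 8% at SD 0.4, with PBV unchanged and PTT = PBV/flow. The exact interval levels and the 6.1e-5 floor need none of those assumptions. No change is called for.

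### Does the Bland-Altman comparison of curve and visual PTT need a stated rule for rest and post-exercise pairs and for independent reads?

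*Combined protocol and SAP*

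**What the plan says.** Aim 4 in Section 2.0 is to "Compare PTT obtained by analysis of time-intensity curves to the PTT estimate obtained by visual assessment". Section 10.0 names the method and nothing more: "Bland-Altman analysis will be used to compare PTT obtained by two different techniques (intensity-time curves and visual assessment". Neither place says whether the comparison is at rest, after exercise, or both.

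Section 6.0 has contrast transit recorded before exercise (step 3) and again after it (step 5): "This administration of contrast will be similar to the pre-exercise PTT measurement". Section 10.0 sets the size: "We will aim for a cohort of 15 participants". There are therefore up to 15 pairs of reads in each state, 30 in all, two per person. The number may be smaller, because "there may be a 'learning curve' that could render data from the initial participants unable to be used in quantitative analyses".

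The primary analysis in Section 10.0 is the within-person comparison of PTT and PBV before and after exercise, by a signed rank test. The agreement analysis is separate from it. No acceptable limit of agreement is set, and no decision in the plan depends on the limits. The documents do not describe the reader, the reading order or blinding for either PTT method.

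**The concern.** Three things make the single sentence look too thin.

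- **Pooling across states.** The rationale in Section 2.0 treats measurement at rest as already achieved and says of the other state that "whether post-exercise data can be reliably obtained and analyzed is unclear". One pooled set of limits would mix the established condition with the uncertain one. It would describe both correctly only if the bias and the SD of the curve-minus-visual differences were the same in each.
- **Two pairs per person.** Treating 30 differences as independent when they come from 15 people would make a confidence interval for the bias too narrow.
- **Independence of the reads.** If the visual value is read with the curve result in view, or the reverse, the errors could be positively correlated and the limits too tight. Once a reader has seen the curve result for a clip, that reader's independent visual read of it is lost.

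At stake is the answer to Aim 4, particularly after exercise: readers of the results might trust the visual shortcut more, or less, than the data justify.

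**Working it through.** The plan states no agreement figure, so there is nothing to reproduce. The only inputs from the documents are 15 participants and two recordings each. All SDs, biases and correlations below are assumptions.

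**1. Pooled limits against true post-exercise limits.** Let the SD of differences be 1 at rest and k after exercise, and let g be the gap in bias between states, in rest SDs. With equal numbers in each state,

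pooled SD = sqrt((1 + k²)/2 + (g/2)²).

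With g = 0:

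- k = 0.5: sqrt(1.25/2) = 0.791; 0.791/0.5 = 1.58. Pooled limits too wide; they contain 99.8% of post-exercise differences.
- k = 1: ratio 1.00; 95.0%.
- k = 2: sqrt(5/2) = 1.581; 1.581/2 = 0.79. Pooled limits too narrow; 87.9%.

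The direction is not fixed by k alone. With k = 1.5 and g = 2, sqrt(3.25/2 + 1)/1.5 = 1.620/1.5 = 1.08, so the limits are too wide although post-exercise error is the larger. When g is not zero, the pooled bias is also simply the average of the two.

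**2. Size against sampling error.** With g = 0, the pooled/post ratio is sqrt((1/k² + 1)/2), which cannot fall below sqrt(1/2) = 0.707. The most that pooling can narrow one post-exercise limit is therefore 1.96 × (1 − 0.707) = 0.57 post-exercise SD. At k = 2 it is 1.96 × (1 − 0.791) = 0.41.

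The 95% CI half-width of a limit from a separate analysis is t(n−1) × sqrt(1/n + 1.96²/(2(n−1))):

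- n = 15: 2.145 × sqrt(0.0667 + 0.1372) = 0.97 SD.
- n = 10 (if early data are lost; this number is assumed): 2.262 × sqrt(0.1 + 0.2134) = 1.27 SD.

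For pooling to shift a limit by more than 0.97 SD, the ratio must exceed 1 + 0.97/1.96 = 1.495. That needs 1/k² > 2 × 1.495² − 1 = 3.47, so k < 0.54. There the pooled limits are too wide, which understates agreement.

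**3. Two pairs per person.** With correlation r between a person's two differences and equal SDs, the true SE of the pooled bias is sqrt(1 + r) times the naive one: 1.14 at r = 0.3 and 1.30 at r = 0.7. Simulated coverage of the nominal 95% interval is about 91% and 86%. This arises only if the pairs are pooled and treated as independent.

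**4. Correlated reads.** If the two methods have equal error SDs and error correlation q, the limits shrink by sqrt(1 − q): 0.84 at q = 0.3 and 0.55 at q = 0.7. The comparison assumes that blinded reads have no shared error. Both methods use the same recording, so some shared error is possible anyway. If blinded reads already correlated at 0.3, moving to 0.7 would give sqrt(0.3/0.7) = 0.65.

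**5. What the text commits to.** Steps 1 and 3 need pooling; step 4 needs one read to be informed by the other. Sections 2.0, 6.0 and 10.0 state neither. Two Bland-Altman analyses, one per state, satisfy Aim 4 and Section 10.0 as written, and would avoid steps 1 and 3 altogether.

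**The case for a change.** The best case for a change is that the silence is selective. Section 10.0 recognises the pairing by state for PTT, PBV and vein-to-heart time, yet says nothing for agreement, where the same two states arise. Choosing the handling after seeing the data weakens it, and reading order cannot be repaired for a reader who has already seen both values. A sentence or two would cost almost nothing.

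Much of this is fair. The gaps are real, the arithmetic is right, and the point about reading order is the strongest part, because a split by state can be made at any time whereas an informed read cannot be undone by the same reader. Even so, contrast passage is recorded, and if clips are kept alongside the data, which Section 12.0 retains for at least six years, another reader could repeat the visual assessment.

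Two supports are weaker than they look. The statement that "there are no current data on (or estimates of) the differences in PTT between rest and exercise" explains the absence of a power calculation. It concerns the change in PTT, not the error between two ways of reading it, so it is no evidence that agreement differs by state. Nor do the obvious remedies fully answer the concern: fixing the visual read first leaves the curve analysis open to influence, and a participant random effect deals with clustering but not with SDs that differ by state.

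**Conclusion.** No change to the plan follows. The omission is real, but it is unstated detail: nothing in the documents specifies pooling, a naive interval or unblinded reading, and no stated rule or figure gives a wrong result. Each harm needs an unfavourable choice that the plan does not make. Separate analyses by state are the natural reading in a study built around a before-and-after comparison.

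The possible size cannot be derived from the documents. Under assumed SD ratios of 0.5 to 2 with equal bias, pooled limits would range from 1.58 down to 0.79 times the true post-exercise width. The optimistic part of that range, at most 0.57 SD per limit, is smaller than the uncertainty of about 0.97 SD that 15 pairs leave in a separate analysis. That comparison does not cover a large bias gap or correlated reads, whose effect depends wholly on assumed correlations.

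The analysis serves one of four aims, lies outside the primary analysis, and feeds no decision rule in a feasibility study without a power calculation. An analyst can be expected to report by state with the number of usable pairs, and to make the visual read without reference to the curve, without the plan being amended.

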11.0 Privacy/Confidentiality Issues

Participant privacy and confidentiality will be protected by the usual practices of the VUMC CRC. The confidentiality of participant data will be protected by maintaining a single master list linking Study ID (from the REDCap database) with Medical Record Number, which will be stored in the REDCap file repository. Any documents or electronic datasheets with identifying information will also be stored in the REDCap file repository. Only the PI and key study personnel will have access to the REDCap database. Given that the participants are likely to be colleagues of study personnel, study personnel will not access participants' charts in the electronic medical record for the purposes of this study except to document participation and consent, as required (i.e. an 'on-study' note).

